| | 
intervention arm) or against a composite reference standard that includes bacteriologically confirmation or/and clinical evidence resulting in therapy initiation.
 
 Diagnostic accuracy of CRP in blood compared to TB symptom's screening in those with microbiologically confirmed TB. 
Comparison of primary and secondary endpoints of the intervention arm with the local standard of care at the sites before the study initiation (a retrospective data collection from consecutive PLHIV admitted at participating hospitals).
 
Sub-analysis
 
 Primary endpoint will be calculated at different intermediate timepoints (48 hours, 7 days and 14 days from enrolment). Primary and selected secondary endpoints will be calculated for participants' subgroups including CD4 cells/mm³ ≥200, <200 and <100, among participants with any TB symptoms, severely ill participants or with AHD, and among participants providing at least one sputum and (or) one urine sample for testing. | | | | | | | | | | | | | | | | | | | | |
| Study Timeline | 
  
 Estimated period for ethics clearance	May / 2022	
 
 Import permits and importation	Jan-May / 2022	
 
 Kick off / training meeting	Nov / 2021	
 
 Estimated date of first participant enrolled:	Sep/ 2022	
 
 Estimated date of last participant enrolled:	Jan/ 2024	
 
 Estimated date of last participant completed:	Mar/ 2024	
 
 Estimated date for end of data cleaning:	May / 2024	
 
 Estimated date for end of data analysis:	July / 2024	
 
 Estimated date for first manuscript draft:	Sep / 2024	
 
 Total duration of study:	47 months	
  
 | Estimated period for ethics clearance | May / 2022 | Import permits and importation | Jan-May / 2022 | Kick off / training meeting | Nov / 2021 | Estimated date of first participant enrolled: | Sep/ 2022 | Estimated date of last participant enrolled: | Jan/ 2024 | Estimated date of last participant completed: | Mar/ 2024 | Estimated date for end of data cleaning: | May / 2024 | Estimated date for end of data analysis: | July / 2024 | Estimated date for first manuscript draft: | Sep / 2024 | Total duration of study: | 47 months |

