10.18 Retrospective data collection

Given that our control arm may not represent the local standard of care across sites, we will compare the main study endpoints of both study arms with a third cohort of patients, which follows the real standard of care at the different sites. We will retrospectively collect data of a cohort of consecutively hospitalized HIV-positive patients that were admitted prior to the trial initiation. Data to allow the evaluation of primary objectives will be collected from medical records (source documents) in an anonymized fashion. We aim to collect data from patients who were admitted to the site two months or more before the day of the trial first study patient recruitment. Patient records will be selected from consecutive admissions from that day backwards until completing the sample size (around 147 cases per site). Data collection will be obtained retrospectively in order to capture the real practice at the different sites, including potential phone calls to confirm the life status of the patients after two months of hospitalization, minimizing the effect of a potential Hawthorne effect. Given the complexity and often impossibility of obtaining informed consent from patients that have been discharged, no informed consent will be sought for these patients. This IC exemption is an exception contemplated in the International Ethical Guidelines for Health-related Research Involving Humans of the Council for International Organizations of Medical Sciences (CIOMS) (Geneva, 2016). The study has not been powered to detect differences in the primary endpoint between intervention or control arm and the retrospective cohort (which may vary between sites). This is a secondary objective that will be analyzed at site level.

11. Schedule of visits (table 2)

| | Day 0 (recruitment) Control arm | Day 0 (recruitment) Intervention arm | Day 0-3 (<72h) | Daily | At discharge If discharged before day 28/56 | Week 4 | Week 8 +/- 3 days |
|--|--|---|-------------------|-------|---|--------|-----------------------------|
| Baseline Evaluation | | | | | | | |
| Informed consent | X | X | | | | | |
| Eligibility criteria verified | X | X | | | | | |
| CD4 count / Viral Load ^{&} | X | X | | | | | |
| Locator information | X | X | | | | | |
| Brief medical history | X | X | | | | | |
| Proof of HIV status stored | X | X | | | | | |
| WHO Symptom screening | X | X | | | X | | |

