From Hospitalization Assessment TB-CAPT-HIV EXULTANT-Hospitalization assessment-v3, and the following versions of this document we will use for the analysis the next variables:

Variable		Used in
label	name	
Date of enrolment	ENROL_D	To calculate the participant's start time
Time of enrolment (24h format)	ENROL_T	
Date of discharge	HOSP_END_D	To calculate the participant's hospitalization time
Time of discharge (24h format)	HOSP_END_T	
Date of lab result: Sputum Ultra	SP_XP_RES_RECEPT_D	To calculate the time to obtain the laboratory results and classify the primary outcome $\leq 72$ h or $> 72$ h for Sputum Ultra sample
Time of lab result: Sputum Ultra	SP_XP_RES_RECEPT_T	

Date of lab result: Urine Ultra	URINE_XP_RES_RECEPT_D	To calculate the time to obtain the laboratory results and classify the primary outcome <= 72h or > 72h for Urine Ultra sample
Time of lab result: Urine Ultra	URINE_XP_RES_RECEPT_T	
Did the patient have cough during hospitalization?	HOSP_COUGH_YN	We will use to describe symptoms.  We will use as a factor variable in modelling
Did the patient have fever (>38°C) during hospitalization?	HOSP_FEVER_YN	We will use to describe symptoms.  We will use as a factor variable in modelling
Did the patient have night sweats during hospitalization?	HOSP_NIGHT_SWEATS_YN	We will use to describe symptoms.  We will use as a factor variable in modelling
Did the patient lose weight during hospitalization?	HOSP_WEIGHT_LOSS_YN	We will use to describe symptoms.  We will use as a factor variable in modelling
Was TB treatment initiated during hospitalization?	HOSP_TB_TX_YN	To calculate the primary objective variable, start treatment within 72h of enrolment
TB treatment initiated, Date and Time	HOSP_TB_TX_START_D HOSP_TB_TX_START_T	
If Yes, AND the patient has a microbiologically confirmed TB diagnosis (question 2.3), was the treatment initiated within 72hrs of enrolment?	HOSP_TB_TX_72H_YN	To determine the proportion of microbiologically confirmed TB cases starting treatment within 72 hours

If wasn't the treatment initiated within 72hrs of enrolment, reason	HOSP_TB_TX_72H_RSN HOSP_TB_TX_72H_RSN_SPEC	To determine the reasons behind starting treatment failure
---	---	--

The laboratory results we will be collected from (15) TB-CAPT-HIV EXULTANT-LabResults-v3- CRF, and the following version of this document. From this source we will select to study the following variables:

Variable		Used in
Label	name	

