### 6.3 Multiple Testing

We consider unnecessary to apply a general adjustment of significance level by multiple comparisons test. We will use the all the statistical power for inference only in the primary study objective. To evaluate the other study endpoints, we use the p-value threshold at 0.05 to find the differences in our study without the objective to extrapolate the results to the global community. However, we will establish a p-value of 0.01 as a threshold for statistical significance in the comparisons related to a) selected secondary efficacy analyses (section 8.2, analyses 8.2.5, 8.2.6, 8.2.7) and subgroup analysis (see section 9.0)

We will adjust the results by site, demographic variables, and other baseline variables if we will detect differences or if these variables have a confounder characteristics profile. To decide this, we will do a preliminary analysis of these variables between sites.

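### SAP 4.4 takes TB symptoms only from the hospital stay, mostly after randomisation, and plans them as model factors, although a Day 0 symptom screen is scheduled in both arms

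*SAP*

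**What the plan says.** In SAP 4.4 the symptom variables come from one form, introduced as "From Hospitalization Assessment TB-CAPT-HIV EXULTANT-Hospitalization assessment-v3, and the following versions of this document". They are HOSP_COUGH_YN ("Did the patient have cough during hospitalization"), HOSP_FEVER_YN ("Did the patient have fever (>38°C) during hospitalization"), HOSP_NIGHT_SWEATS_YN and HOSP_WEIGHT_LOSS_YN, all with the same time window. Each has two stated uses: describing symptoms, and "We will use as a factor variable in modelling". The variables that SAP 4.4 selects from the Baseline Characteristics form include no TB symptom.

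The visit schedules in Protocol section 11 and SAP 4.1 both list "WHO Symptom screening" under baseline evaluation on Day 0 in both arms, with a further mark at discharge.

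On adjustment, SAP 6.3 says: "We will adjust the results by site, demographic variables, and other baseline variables", if differences are detected or the variables look like confounders. The sub-analysis list in the protocol synopsis includes the primary and selected secondary endpoints "among participants with any TB symptoms".

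**The concern.** A covariate or subgroup in a randomised comparison should be fixed before the arms can influence it. A symptom recorded at any time up to discharge is not. The intervention aims to bring TB treatment forward, and treatment can change symptoms. Staff know the arm and the test results (Protocol 10.6, SAP 4.3), so a positive result can change what is asked and written down. Conditioning on such a variable gives up part of the protection of randomisation, and the direction of the resulting bias is not known in advance.

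The items also differ in content from the symptom criteria at entry. Weight lost on the ward is not weight loss at presentation. The in-stay fever item has a threshold of 38°C, while the symptom criterion in Protocol section 9 names fever without one.

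If the wording stands, the analyst has only post-baseline symptom variables to hand when a symptom factor is wanted. Any later choice between two symptom definitions could be made with results in view.

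**Working it through.** The plan gives no figure on this point, so the main check sets the sections side by side.

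1. **Time window.** Randomisation is on the day of enrolment, Day 0 (SAP 4.3). Protocol 10.4 wants enrolment preferably within 12–24 hours of admission. The stay can run well past that: Protocol 10.10 allows for participants still in hospital at week 4 or week 8. The primary endpoint is decided at 72 hours. An in-stay symptom can therefore first appear after the primary endpoint is already fixed.

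2. **Is there a pre-randomisation alternative?** Both schedules have the Day 0 screen in both arms. Protocol 10.4 has baseline forms completed before arm-specific procedures, and Protocol 14.1 lists TB symptoms among the data collected. Control-arm testing under Protocol 10.9.2 needs symptom status in any case.

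3. **Where could the in-stay symptoms enter?**
   - SAP 8.1, primary: unadjusted z-test on a difference of proportions, stratified by country and CD4. No symptom term.
   - SAP 8.2.1, 8.2.3–8.2.6, 8.2.8, 8.2.9: comparisons of proportions. No symptom term.
   - SAP 8.2.7: covariates named as site, sex and CD4 from the baseline form. No symptom term.
   - SAP 8.2.2: optional Cox model, covariates not named. Open.
   - SAP 6.3: baseline variables, chosen after a preliminary look. SAP 4.4 selects no baseline symptom, so a symptom adjustment would have to draw on the in-stay items, against the rule's own wording.
   - SAP 9: subgroups by country or site, CD4, viral load and sex. No symptom subgroup.
   - Protocol synopsis: subgroup with any TB symptoms. The SAP selects no Day 0 variable to define it.

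4. **Illustration of size, on assumed rates.** The planning proportions are 19% and 26% (SAP 5), a difference of 26 − 19 = 7.0 points. The documents give no symptom rates. Assume the symptom occurs during the stay in a share s0 of participants without the primary outcome and s1 of those with it, the same in both arms. For stratum S (symptom yes or no), let n1 and n0 be the intervention and control shares in S. The stratified difference is Σ w·RD / Σ w, with w = n1·n0/(n1 + n0).

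   Example with s0 = 0.50 and s1 = 0.95:
   - Symptom present: intervention 0.26×0.95 = 0.2470 with the outcome and 0.74×0.50 = 0.3700 without, so n1 = 0.6170. Control 0.19×0.95 = 0.1805 and 0.81×0.50 = 0.4050, so n0 = 0.5855. RD = 0.4003 − 0.3083 = 0.0920; w = 0.3004.
   - Symptom absent: n1 = 0.0130 + 0.3700 = 0.3830; n0 = 0.0095 + 0.4050 = 0.4145. RD = 0.0339 − 0.0229 = 0.0110; w = 0.1991.
   - Stratified difference = (0.3004×0.0920 + 0.1991×0.0110)/(0.3004 + 0.1991) = 0.0598, or 6.0 points.

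   The symptom is now unbalanced between arms (61.7% against 58.6%) only because it follows the outcome. Over s0 = 0.50–0.70 and s1 = 0.30–0.95 the result runs from 5.98 to 7.00 points. A Day 0 symptom is balanced in expectation by randomisation and leaves the difference at 7.0.

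**The case against.** The strongest reply is that no analysis specified in the SAP uses these variables. That stands for the primary test, the comparisons of proportions, the SAP 8.2.7 models and the SAP 9 subgroups. SAP 6.3, read literally, keeps post-baseline variables out of adjusted comparisons. The modelling note names neither a model nor a role, whereas the country row in SAP 4.4 does speak of adjusting regression models. A model that only describes correlates of treatment start would not bias an arm contrast. Still, the note is a stated use, given for all four symptoms, and SAP 8.2.2 leaves its covariates open. It needs to be closed.

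Two further replies also stand. SAP 4.4 lists only selected variables: age is missing from it but appears in SAP Table 1. The absent baseline symptom item therefore does not show that the data are not collected. And the window includes the hours before enrolment, so a symptom present on Day 0 that persists is coded yes. The window is mostly, not wholly, after randomisation.

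A reader might infer a head count of misclassified controls from Protocol 13.1, which expects up to 10% of controls to go untested by either Ultra or LAM. The documents do not support this. Being untested is not the same as meeting no testing criterion. Meeting no criterion is not the same as being symptom-free, since a symptom-free control with CD4 below 200 qualifies for LAM. No rate of symptoms arising in hospital is given. Nor is there a planned no-symptom subgroup to be harmed. The comparison of CRP with symptom screening belongs to the separate exploratory plan (Protocol 13.2.3, SAP 3.2).

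**Conclusion.** The concern holds in a limited form. The SAP selects TB symptoms only from a window that is mostly after randomisation in an unblinded trial, and it marks them for modelling while a Day 0 screen is scheduled in both arms. Used in an arm comparison, they can bias it, and they do not fit the SAP's own rule on baseline adjustment.

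A reader might infer that the primary result is at risk. It is not, as written: that test is unadjusted. The exposure is confined to models with unnamed covariates, chiefly the optional Cox model in SAP 8.2.2, and to the synopsis's symptom subgroup. That subgroup is not repeated in Protocol 13.2.3 or SAP 9, and neither document says the in-stay items would define it.

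The shift from 7.0 to at lowest 6.0 points is an illustration only. It rests on assumed symptom rates and on the same link between symptom and outcome in both arms. It does not cover recording that differs by arm, for which neither size nor direction can be given.

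**What to change.** In SAP 4.4:

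- Add the Day 0 WHO symptom screen to the selected baseline variables, as the SAP's symptom variable.
- State that only this variable is used for any adjustment or symptom subgroup in comparisons between arms, including any Cox model under SAP 8.2.2 and the synopsis's symptom subgroup if it is kept.
- Keep the four HOSP_ symptom variables for description, and delete the modelling note from their rows.

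The cost is SAP wording. No new data should be needed, because the screen is already scheduled for both arms. The Baseline Characteristics form is not among the documents, so the sponsor should confirm that it records the Day 0 screen item by item. Make the change before database lock.

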8.2 Secondary endpoints

- Eight-week all-cause mortality (main secondary endpoint) among all participants enrolled. The numerator will be number of deaths during eight weeks after enrolment, the denominator is the number of participants enrolled. We will compare this indicator between both study arms. In addition, this endpoint will also be calculated considering right censored observation when a participant is lost to follow up during the observation period or a

This project is part of the EDCTP2 programme supported by the European Union

participant experiences a different event that makes further follow up impossible.

- Time to TB treatment initiation among microbiologically confirmed cases and among all TB cases since enrolment. We will estimate Kaplan Meier curves (event= TB treatment initiation among laboratory confirmed TB patients and among all TB cases) and hazard ratios at day 7, 14, 28 and 56. Additionally we will compare the time to related estimates (mean and standard deviation) of intervention and control group.
- Proportion of cases re-admitted to hospital. The numerator will be the number of admissions after initial discharge and within 8 weeks from enrolment. The denominator will be the number of participants enrolled.
- The proportion of participants who are diagnosed with TB (irrespective of bacteriological confirmation) and started TB treatment within 72 hours of enrolment. The numerator is the number of participants diagnosed with TB (with or without bacteriological confirmation) who started treatment within 72 hours of enrolment; the denominator is the number of participants enrolled.
- The proportion of participants who are diagnosed with microbiologically confirmed TB and are started on treatment at 7 days, 14 days, 4 weeks and 8 weeks of enrolment. In addition, this endpoint will also be calculated considering right censored observation when a participant is lost to follow up or dead during the observation period or a participant experiences a different event that makes further follow up impossible.
- Proportion of participants who are able to provide sputum, stool and urine samples for Ultra/AlereLAM testing within 24, 48 and 72 hours of enrolment (the numerator is the number of urine samples or (and) sputum samples provided within 72 hours of admission and the denominator is the number of patients enrolled).

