10.10 Follow up procedures (table 2)

Hospitalization stay (daily)

During hospitalization (daily) and at discharge, study team will verify and record whether a TB diagnosis has been made and/or anti TB treatment started. The study team will be working jointly with the routine health care staff so clinical decisions are made jointly. Study team will also record any ad-hoc TB investigation (additional Ultra, LAM testing, X-ray, etc) and their result. HIV care will follow national guidelines. .

Scheduled visits

After enrolment, there are two scheduled visits that need to take place unless the patient remains hospitalized (week 4 and week 8). These visits can occur either in the outpatient clinic, as home visits or by call or video-call depending on the patient and team preferences and COVID-19 epidemiologic situation. However, outpatient visits are recommended. A member of the study team will verify whether a TB diagnosis has been made on the relevant medical records (hospital or NTP office) and/or anti TB treatment started after discharge. Study staff will also record any ad-hoc TB investigation that was initiated by the care provider for clinical reasons (additional Ultra, LAM testing, X ray, etcetera) and their result (both by checking patient records and by asking the patient). HIV care will follow national guidelines. Vital status will also be recorded at these two visits. These visits will have a window period of -/+ 3 days (at week 4) and -3/+7 days at week 8.

In case a discharged participant does not attend the week 4 or week 8 visit, three phone call attempts will be made and, if unsuccessful, at least one home visit will be performed in order to collect relevant data to that visit. These attempts should be recorded in a patient tracking log. Week 4 visit should be sought until week 8 window visit opens, although will be considered a protocol deviation if done outside the week 4 window visit.

This project is part of the EDCTP2 programme supported by the European Union

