10.11 Participant study completion (week 8)

Patients might terminate their participation in the study at any point. Reason, if available, should be recorded in the patient file. Once participants have completed their week 8 visit (at the hospital/outpatient clinic or as home visit), they will be considered having completed their participation in the study. For those not attending week 8 visit, they will be considered lost to follow up after the three phone call attempts and home visit have occurred. Deaths occurring during the study at patient's household will be documented and relatives will be asked about signs and symptoms before death. In settings where verbal autopsies are routinely conducted (CISM), this data will be considered a study source document and information captured in the off-study-form.

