14.2 CRFs

We have developed 10 main CRFs for all participants:

- Consent & Eligibility CRF
- Baseline Characteristics CRF
- Specimen Collection CRF
- AlereLAM & CRP CRF
- FujiLAM Results CRF
- Xpert Ultra Tongue Swab Results CRF
- Lumira Dx Test Results CRF
- Hospitalization assessment CRF
- 4 Week visit CRF
- 8 Week visit CRF
- Lab results CRF (including TB specific and other lab results (CD4 counts, viral load)
- Study Completion CRF (whenever a patient stops being part of the study (completed all procedures -at week 8), death before week 8, or LTFU at any point within the first 8 weeks).

This project is part of the EDCTP2 programme supported by the European Union

In addition, a retrospective local standard of care CRF will be used (Retrospective CRF).

The Lab result CRF might be used at any point within the study period if additional TB tests are performed on the patient.

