Karnofsky Performance Status Scale	KARNOFSKY	To describe the participant's profile.  For previous analysis about at random lost to follow up.
Patient's WHO clinical Stage	WHO_STAGES	To describe the participant's profile.  For previous analysis about at random lost to follow up.
TB treatment start	TB_TX_START_YN	To describe the participant's profile.  For previous analysis about at random lost to follow up.
Random group	RANDOM_ASSIGN	For previous analysis about at random lost to follow up.
Date of randomization	RANDOM_D	To calculate endpoints related to time.

The Follow-up week4 participants variables will be collected from TB-CAPT-HIV EXULTANT-Week-4-v3 CRF, and the following versions of this document. From this CRF the important variables for the analysis are:

Variable		Used in
label	name	
Is the visit taking place? (y/n)	W4_VISIT_YN	To calculate the number of people who come to visit at week 8
Is the visit taking place?, date	W4_VISIT_D	To calculate the time in the study, to draw the study K-M graphs in group of people who come to this visit.
If the patient has died, date of death	W4_DEATH_D	To use in the K-M graphs as an endpoint for these participants.
Has the patient started TB treatment since discharge?	W4_TB_TX_YN	To calculate the proportion of main study objective
Has the patient started TB treatment since discharge?, date	W4_TB_TX_START_D	To calculate the proportion of people started on treatment.
Has the patient abandoned TB treatment since last visit?	W4_TB_TX_END_YN	To calculate the failure TB treatment

The Follow-up week8 participants variables will be collected from TB-CAPT-HIV EXULTANT-Week-8-v3 CRF, and the following versions of this document. From this CRF the important variables for the analysis are:

Variable		Used in
label	name	
Is the visit taking place? (y/n)	W8_VISIT_YN	To calculate the number of people who come to visit at week 8

Is the visit taking place? (date)	W8_VISIT_D	To calculate the time in the study, to draw the study K-M graphs in group of people who come to this visit.
If the patient has died, date of death	W8_DEATH_D	To use in the K-M graphs as an endpoint for these participants.
Has the patient started TB treatment since discharge?	W8_TB_TX_YN	To calculate the proportion of main study objective
Has the patient started TB treatment since discharge?, date	W8_TB_TX_START_D	To calculate time at risk
Has the patient abandoned TB treatment since last visit?	W8_TB_TX_END_YN	To calculate the failure TB treatment

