Date of sample collection	SAMP_COL_D	To check the range of dates in context of our research objectives
CD4 results	CD4_RES	To analyse the primary objective stratified by this variable
Viral load results	VL_RES	To analyse the primary objective stratified by this variable
Sputum Xpert Ultra	SP_XP_RES	To determine whether a patient is microbiologically confirmed
Urine Xpert Ultra	URINE_XP_RES	To determine whether a patient is microbiologically confirmed
Stool Xpert Ultra	STOOL_XP_RES	To determine whether a patient is microbiologically confirmed
Xpert Ultra in another specimen I	S1_XP_RES	To determine whether a patient is microbiologically confirmed
Xpert Ultra in another specimen II	S2_XP_RES	To determine whether a patient is microbiologically confirmed

The AlereLAM Results will come from the TB-CAPT-HIV EXULTANT-AlereLAM & CRP v3 form, and the update versions of this document. From this CRF will be get:

Variable		Used in
Label	name	
AlereLAM result	ALERE_RES	To determine whether a patient is microbiologically confirmed To do the sensibility analysis of test
If results available, date	ALERE_RES_D	To calculate the lab results time
If results available, time	ALERE_RES_T	
If results not available, reason	ALERE_RES_YN_RSN	To calculate the proportion and reasons of no AlereLAM result

The Study Completion participants variables we will collected from TB-CAPT-HIV EXULTANT-StudyCompletion-v3 form, and the following versions of this document. From this CRF the important variables for the analysis are:

Variable		Used in
Label	name	
Did participant complete the study procedures at study visit week 8?	VISIT_WK8_D	To calculate the proportion of endpoints at week 8
Did participant complete the study procedures at study visit week 8? date	VISIT_WK8_D	To calculate the time in the study, to draw the study K-M graphs
If not, and the participant withdrew, was withdrawn, dropped out or died during the study, indicate the primary reason	END_RSN	To calculate the proportion deaths, lost to follow-up, withdraws and complete study

Date participant completed, withdrew, was withdrawn/excluded or dropped out from study, date	END_D	To calculate the time in the study, to draw the study K-M graphs
--	-------	--

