## 7.2 Derived variables

We will create some derived variables according to solve the study hypothesis, some of them we will describe in the following SAP versions.

The variables that we will create are:

New Variable	Type	Values
Type of Employment	Categorical	0: Unemployed for any reason 1: Health care worker 2: Prison warder or work at a correctional facility 3: Miner
Time from last HIV+ result	Continuous	0 to randomization date
Time of follow-up	Continuous	From randomization date to end study completion date
Time to TB treatment initiation (in hours)	Continuous	From randomization date to start TB treatment date
ITT cohort	Categorical	0: Not included in ITT 1: Included in ITT
ATP cohort	Categorical	0: Not included in ATP 1: Included in ATP
Participants diagnosed with microbiologically confirmed TB	Categorical	0: No 1: Yes
Participants diagnosed with microbiologically confirmed TB and started on TB treatment within 72 hours of enrolment	Categorical	0: No 1: Yes
CD4 (binary)	Categorical	0: CD4 count <100

	1: CD4 count >=100
--	--------------------

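### Kaplan-Meier follow-up ends at a study-exit date that is undefined for lost participants; if it is the date loss is declared, they count as event-free to about day 56

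*SAP*

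**What the plan says.** **Follow-up time.** The Study Completion table in SAP 4.4 lists END_D, labelled "Date participant completed, withdrew, was withdrawn/excluded or dropped out from study, date", with the purpose "To calculate the time in the study, to draw the study K-M graphs". SAP 7.2 defines time of follow-up as "From randomization date to end study completion date". The week-4 and week-8 visit dates also feed the curves, but only "to draw the study K-M graphs in group of people who come to this visit". Death dates enter as endpoints. The discharge date is listed only for length of stay. No last-contact or last-known-alive date is derived.

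**When loss is declared.** Protocol 10.10 requires three calls and at least one home visit after a missed week-4 or week-8 visit, and keeps the week-4 visit open until the week-8 window opens. On windows it says: "These visits will have a window period of -/+ 3 days (at week 4) and -3/+7 days at week 8". For those who miss week 8, protocol 10.11 says "they will be considered lost to follow up after the three phone call attempts and home visit have occurred". Protocol 14.2 lists among the uses of the Study Completion form "LTFU at any point within the first 8 weeks".

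**Analyses that need a censoring date.** Protocol 8.2 also plans eight-week mortality "considering right censored observation when a participant is lost to follow up during the observation period", and 13.2.2 plans Kaplan-Meier curves and a log-rank test for time to mortality. SAP 8.2.2 and 8.2.7 plan Kaplan-Meier analyses of time to treatment and time to diagnosis. SAP 8.2.1 and 8.2.8 compare proportions of deaths only.

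**The concern.** A Kaplan-Meier estimate treats a person as observed and event-free until the censoring date. That is right only if status was known up to that date. An administrative exit date set after a failed search is later than the last date on which anyone knew the participant's status.

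Suppose a participant is discharged on day 8 and never reached again, and loss is declared at day 56. That person sits in the mortality and diagnosis risk sets for 48 unobserved days. A TB case who had not started treatment would stay in the treatment risk set in the same way.

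The stake is the purpose of the censored analysis. The crude proportion counts every lost participant as a survivor, and the protocol adds the censored version to relax that. If lost participants leave only after day 56, the censored version makes the same assumption about them. Mortality at eight weeks is the protocol's main secondary endpoint. The primary 72-hour endpoint is not affected.

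**Working it through.** **Step 1: the date implied by the procedures.** Week 8 is day 56, so the window runs from 56 − 3 = day 53 to 56 + 7 = day 63. Because the week-4 visit is sought until that window opens, and loss at week 8 follows failed calls and a home visit, the ordinary declaration date is day 53 or later. An exit on days 53 to 55 would drop a lost person just before day 56, with little effect.

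**Step 2: inputs.** From the documents: 586 per arm (SAP 5) and 5% loss at month 2 (protocol 10.12), so 0.05 × 586 = 29 lost per arm and 557 followed. The documents give no mortality figure and no censored estimate to reproduce. Assumed: eight-week mortality of 15-30% among those followed, constant hazard, and loss unrelated to outcome.

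**Step 3: one case by hand, 20% mortality.** Deaths = 0.20 × 557 = 111. At constant hazard, 59 fall by day 28 and 52 later.

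- Crude: 111/586 = 18.94%.
- Lost censored at day 60: nobody leaves the risk set before day 56 except by death, so survival is (586 − 111)/586 and mortality is 18.94%, identical to crude.
- Lost censored at day 28: survival = (527/586) × (446/498) = 0.8054, mortality 19.46%.
- Lost censored at day 7 (15 deaths before, 96 after): survival = (571/586) × (446/542) = 0.8018, mortality 19.82%.

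**Step 4: the range, 5% loss.**

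| Assumed mortality | Deaths | Crude | Lost censored day 60 | Day 28 | Day 7 |
|---|---|---|---|---|---|
| 15% | 84 | 14.33 | 14.33 | 14.72 | 15.00 |
| 20% | 111 | 18.94 | 18.94 | 19.46 | 19.82 |
| 25% | 139 | 23.72 | 23.72 | 24.39 | 24.82 |
| 30% | 167 | 28.50 | 28.50 | 29.31 | 29.83 |

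The understatement is 0.4 to 0.8 points if last contact was day 28, and 0.7 to 1.3 points if it was day 7.

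**Step 5: a different time pattern.** Assume half of deaths occur by day 10, deaths are uniform within each period, and last contact is uniform over days 5 to 14. The share of deaths after last contact averages 0.625 for contacts on days 5-10 and 0.478 for days 10-14. Weighted, (5 × 0.625 + 4 × 0.478)/9 = 0.56. The understatement is loss × 0.56 × mortality. At 5% loss this is 0.42, 0.56 and 0.84 points at 15, 20 and 30% mortality.

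**Step 6: the between-arm difference.** With equal, non-informative loss, both levels shrink by the same factor (1 − 0.05 × 0.56 = 0.97), so the error largely cancels. With an assumed 3% versus 10% loss and equal true mortality, the false difference is (0.10 − 0.03) × 0.56 × mortality: 0.6, 0.8 and 1.2 points at 15, 20 and 30%. For scale, at 20% mortality the standard error of the difference is √(2 × 0.20 × 0.80/586) = 2.3 points.

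**Step 7: informative loss.** If all 29 lost participants in an arm had died, crude mortality would be understated by 29/586 = 4.9 points.

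**The case against.** The strongest reply is that the documents never say END_D is the declaration date. Its label can equally mean the day a person dropped out. Protocol 14.2 provides for loss at any time in the eight weeks, and 8.2 speaks of loss within the observation period. This stands: a reader might infer that END_D always falls after the failed week-8 search, but the form instructions are not in the documents and the point is conditional on that reading. It is still the natural reading of 10.10 and 10.11, and no other date is specified for someone who misses visits.

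A reader might also infer that nobody is censored before day 56, so that the censored analysis corrects nothing. That is too broad: withdrawn and excluded participants have their own earlier dates. The identity in step 3 applies to lost participants.

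A third inference is that protocol 14.2 contradicts 10.11. The two can coexist, since one lists occasions for completing a form and the other defines loss for those who miss week 8. What is missing is a rule for dating the loss.

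It is also fair to say that SAP 8.2 contains no censored mortality analysis for END_D to distort. The protocol promises one and the SAP omits it, which is a gap to close at the same time. Finally, the effect is modest: 0.8 points is about a third of a standard error, repeated searches and record checks should limit the unobserved time, and protocol 13.2.2 and SAP 10 already compare lost with retained participants. Those comparisons do not repair a wrong censoring date.

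**Conclusion.** The SAP ends Kaplan-Meier follow-up at a study-exit date and does not define that date for lost participants. If it is the date loss is declared, the lost are counted as event-free to about day 56, and the protocol's censored mortality estimate equals the crude proportion as far as they are concerned. The diagnosis curves, and the treatment curves among TB cases, have the same flaw; its size there was not calculated.

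For mortality, the understatement is roughly 0.4 to 1.3 points per arm. This assumes 15-30% mortality, 5% non-informative loss and last contact between the first week and day 28. A reader might infer a false treatment effect, but the documents do not support that as an expectation: it needs unequal or informative loss, and they anticipate 5% overall. At an assumed 3% versus 10% loss it would be about 0.6 to 1.2 points. Unequal loss cannot be excluded in an unblinded trial. Censoring at last verified status corrects the non-informative part only; it does not remove bias from loss related to death.

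**What to change.** - In SAP 4.4 and 7.2, end follow-up for each time-to-event analysis at the earliest of the event, the last date the relevant status was verified, and day 56. For mortality this is the last date known alive. For diagnosis and treatment it is the last verification of that status, including the hospital or TB programme record checks in protocol 10.10, which may be later than the last personal contact.
- Use END_D for participant disposition only.
- Add the right-censored mortality analysis of protocol 8.2 and 13.2.2 to SAP 8.2.
- State in protocol 14.2 that loss is declared and dated consistently with 10.10 and 10.11.

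The cost is a few sentences and one derived date per endpoint, built from contacts and record checks the protocol already requires. No visits are added. The rule should be fixed before database lock, so that the censoring date is not chosen with outcomes in view.
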